3.1.4 ECOG performance status ≤ 1 (see **Appendix A**)

3.1.5 Participants must have normal organ and marrow function as defined below:

- Absolute neutrophil count $\geq 1,500/\text{mcL}$
- Platelets $\geq 100,000/\text{mcL}$
- Total bilirubin $\leq 1.5 \times$ institutional upper limit of normal (ULN)
- AST(SGOT)/ALT(SGPT) $\leq 2.5 \times$ institutional ULN, **OR**

- AST(SGOT)/ALT(SGPT) $\leq 5 \times$ institutional ULN if liver metastases are present
- Serum creatinine $\leq 1.5 \times$ institutional ULN, **OR**
- Creatinine clearance $\geq 60 \text{ mL/min}/1.73 \text{ m}^2$ for participants with serum creatinine levels above $1.5 \times$ institutional ULN.

3.1.6 Ability to understand and the willingness to sign a written informed consent document.

3.1.7 Participants must be able and willing to undergo a pre-treatment tumor tissue biopsy. Participants must also be willing to undergo an on-treatment tumor tissue biopsy if clinically feasible.

3.1.8 Participants must have a tumor tissue sample available (formalin-fixed paraffin embedded [FFPE] tissue block or unstained slides); may be newly obtained or obtained within 6 months prior to enrollment (without systemic therapy given after the sample was obtained). Participants without sufficient archival tissue may be enrolled following successful completion of the pre-treatment tumor tissue biopsy. Tissue must be a core needle biopsy, excisional, or incisional biopsy. Fine needle aspirates (FNA) or malignant effusions are not adequate. Bone biopsies without a soft tissue component are not adequate.

3.1.9 The effects of nivolumab and ipilimumab on the developing human fetus are unknown. For this reason, women of childbearing potential (WOCBP) must agree to follow instructions for acceptable contraception from the time of signing consent, and for 23 weeks after their last dose of protocol-indicated treatment. Should a woman become pregnant or suspect she is pregnant while she or her partner is participating in this study, she should inform her treating physician immediately. Men treated or enrolled on this protocol who are not azoospermic who are sexually active with WOCBP must agree to follow instructions for acceptable contraception from the time of signing consent, and for 31 weeks after their last dose of protocol-indicated treatment.

3.2 Exclusion Criteria

3.2.1 Participants with known *EGFR* mutations or *ALK* rearrangements. All subjects must have been tested for *EGFR* mutation and *ALK* rearrangement prior to study entry, unless they are known to have a *KRAS* mutation.
Note: molecular testing is not required for squamous NSCLC.

3.2.2 Participants who have had prior treatment with an anti-PD-1, anti-PD-L1, anti-PD-L2, anti-CTLA-4 antibody, or any other antibody or drug specifically targeting T-cell co-stimulation or checkpoint pathways.

3.2.3 Participants who received prior non-CNS directed palliative radiation therapy within 7 days of the date of study entry.

- 3.2.4 Participants who are receiving any other investigational agents.
- 3.2.5 Participants with known untreated brain metastases should be excluded from this clinical trial because of their poor prognosis and because they often develop progressive neurologic dysfunction that would confound the evaluation of neurologic and other adverse events. Subjects are eligible if CNS metastases are adequately treated and subjects are neurologically returned to baseline (except for residual signs or symptoms related to the CNS treatment) for at least 2 weeks prior to study entry. Subjects must be either off corticosteroids, or on a stable or decreasing dose of ≤ 10 mg daily prednisone (or equivalent) for at least 2 weeks prior to first study treatment.
- 3.2.6 History of allergic reactions attributed to compounds of similar chemical or biologic composition to ipilimumab or nivolumab.
- 3.2.7 Participants with previous malignancies are excluded unless a complete remission was achieved at least 2 years prior to first treatment and no additional therapy is required or anticipated to be required during the study period as judged by the treating investigator. Exceptions include non-melanoma skin cancers, and *in situ* cancers of any type (e.g. bladder, gastric, colon, cervical/dysplasia, melanoma, or breast carcinoma *in situ*).
- 3.2.8 Participants with any other active malignancy requiring concurrent intervention.
- 3.2.9 Participants with an active, known, or suspected autoimmune disease. Subjects with type I diabetes mellitus, hypothyroidism only requiring hormone replacement, skin disorders (such as vitiligo, psoriasis, or alopecia) not requiring systemic treatment, or conditions not expected to recur in the absence of an external trigger are permitted to enroll.
- 3.2.10 Participants with a condition requiring systemic treatment with corticosteroids of > 10 mg daily prednisone (or equivalent), or subjects requiring other immunosuppressive medications within 14 days of first treatment. Inhaled, topical, ophthalmologic, local steroid injections, and adrenal replacement steroid > 10 mg daily prednisone or equivalent are permitted in the absence of active autoimmune disease.
- 3.2.11 Participants with interstitial lung disease that is symptomatic or may interfere with the detection or management of suspected drug-related pulmonary toxicity in the opinion of the treating investigator.
- 3.2.12 Participants with a known history of testing positive for human immunodeficiency virus (HIV), or known acquired immunodeficiency syndrome (AIDS).
- 3.2.13 Participants with known positive test for hepatitis B or C indicating acute or chronic infection.
- 3.2.14 Participants with \geq Grade 2 peripheral neuropathy.

- 3.2.15 Uncontrolled intercurrent illness including, but not limited to, ongoing or active infection, symptomatic congestive heart failure, unstable angina pectoris, cardiac arrhythmia, or psychiatric illness/social situations that would limit compliance with study requirements.
- 3.2.16 Pregnant women are excluded from this study because ipilimumab and nivolumab are both agents with the potential for teratogenic or abortifacient effects. Because there is an unknown but potential risk for adverse events in nursing infants secondary to treatment of the mother with ipilimumab or nivolumab, breastfeeding should be discontinued if the mother is treated with ipilimumab or nivolumab. A negative serum pregnancy test is required prior to study entry.

3.3 Inclusion of Women and Minorities

Both men and women of all races and ethnic groups are eligible for this trial.

4. REGISTRATION PROCEDURES

4.1 General Guidelines for DF/HCC Institutions

Institutions will register eligible participants in the Clinical Trials Management System (CTMS) OnCore. Registrations must occur prior to the initiation of protocol therapy. Any participant not registered to the protocol before protocol therapy begins will be considered ineligible and registration will be denied.

An investigator will confirm eligibility criteria and a member of the study team will complete the protocol-specific eligibility checklist.

Following registration, participants may begin protocol therapy. Issues that would cause treatment delays should be discussed with the Overall Principal Investigator (PI). If a participant does not receive protocol therapy following registration, the participant's registration on the study must be canceled. Registration cancellations must be made in OnCore as soon as possible.

4.2 Registration Process for DF/HCC Institutions

DF/HCC Standard Operating Procedure for Human Subject Research Titled *Subject Protocol Registration* (SOP #: REGIST-101) must be followed.

5. TREATMENT PLAN

5.1 Treatment Regimen

Nivolumab will be administered once every 2 weeks, on cycle days 1, 15, and 29. Ipilimumab will be administered once every 6 weeks, on cycle day 1. A treatment cycle is defined as 6 weeks or 42 days. Treatment will be administered on an outpatient basis. Reported adverse events and potential risks are described in **Section 7**. Appropriate dose modifications are described in **Section 6**.

Table 3: Regimen Description					
Agent	Premedications	Dose^A	Route^B	Schedule	Cycle Length
Ipilimumab	None	1 mg/kg	IV over 60 minutes (\pm 5 minute infusion window)	Day 1	42 days (6 weeks)
Nivolumab	None	3 mg/kg	IV over 60 minutes (\pm 5 minute infusion window)	Days 1, 15, 29	

A. Calculation of body surface area (BSA) should be performed per institutional standards of practice. Re-calculation of dosage for fluctuations in body weight should be made in accordance with institutional guidelines.
 
B. On days where both nivolumab and ipilimumab will be administered, nivolumab should be administered first. The ipilimumab infusion will start at least 30 minutes after completion of the nivolumab infusion.
					

5.2 Pre-Treatment Criteria

5.2.1 Cycle 1, Day 1

If screening laboratory values were completed \leq 96 hours before Cycle 1 Day 1, laboratory tests do not need to be repeated on Cycle 1 Day 1 and the screening laboratory values may be used as the Cycle 1 Day 1 values.

If screening laboratory values were completed $>$ 96 hours prior to Cycle 1 Day 1, laboratory tests must be repeated on Cycle 1 Day 1. Laboratory values drawn on Cycle 1 Day 1 must re-meet eligibility criteria, exceptions to this are possible following discussion with the principal investigator.

5.2.2 Subsequent Cycles

Management of specific toxicities considered at least possibly related to the study regimen is outlined in **Section 6**.

5.3 Agent Administration

5.3.1 Nivolumab

Nivolumab will be administered as an IV infusion over approximately 60 minutes (\pm 5 minute infusion window). Nivolumab will be administered every 2 weeks, on cycle days 1, 15, and 29. On days where both nivolumab and ipilimumab will be administered, nivolumab should be administered first. The ipilimumab infusion will start at least 30 minutes after completion of the nivolumab infusion.

5.3.2 Ipilimumab

Ipilimumab will be administered as an IV infusion over approximately 60 minutes (\pm 5 minute infusion window). Ipilimumab will be administered every 6 weeks, on cycle day 1. BSA for dosage calculations should be performed per institutional standards of practice. Re-calculation of dosage for fluctuations in body weight should be made in accordance with institutional guidelines. On days where both nivolumab and ipilimumab will be administered, nivolumab should be administered first. The ipilimumab infusion will start at least 30 minutes after completion of the nivolumab infusion.

5.4 General Concomitant Medication and Supportive Care Guidelines

No investigational or commercial agents or therapies other than ipilimumab and nivolumab may be administered with the intent to treat the participant's malignancy, with the exception of palliative radiation therapy with the principal investigator's agreement. As concurrent radiotherapy and nivolumab/ipilimumab have not been formally evaluated, in cases where palliative radiotherapy is required for a tumor lesion, then nivolumab/ipilimumab should be withheld for at least 1 week before, during, and 1 week after radiation. Bisphosphonate use is permitted.

Investigators should use appropriate supportive medications to address toxicities that arise during the study, including but not limited to antiemetics, corticosteroids, and blood product transfusion.

5.4.1 Infusion-Related Reactions

Infusion reactions, including high-grade hypersensitivity reactions, following administration of nivolumab or ipilimumab are uncommon. Participants should be monitored for fever, chills, rigors, itching, arthralgias, rash, hypertension, hypotension, bronchospasm, and dyspnea during and immediately after administration of the study agents.

In the event of any \geq Grade 3 infusion-related reaction, protocol therapy should be permanently discontinued. Emergency care should be implemented as clinically appropriate and per local institutional standards of practice.

In the event of any Grade 1 infusion-related reaction, the patient should be monitored until recovery of symptoms to baseline. The following prophylactic premedications are recommended for future infusions: diphenhydramine 25 – 50 mg (or equivalent) and/or acetaminophen 325 to 1000 mg (or equivalent) at least 30 minutes before additional infusions.

In the event of any Grade 2 infusion-related reaction, the infusion should be stopped. The patient may be medicated with diphenhydramine 50 mg IV (or equivalent) and/or acetaminophen 325 – 1000 mg PO (or equivalent). Corticosteroids or bronchodilators may also be administered as clinically appropriate. The patient should be monitored until symptoms have resolved to baseline. After resolution of symptoms, the infusion may be restarted at 50% of the original infusion rate. If no further complications ensue after 30 minutes, the rate may be increased to

100% of the original infusion rate. If symptoms recur, no further administration of nivolumab or ipilimumab should occur at that visit. Administer 50 mg IV diphenhydramine (or equivalent) and monitor patient until the symptoms resolve to baseline.

For future infusions following a Grade 2 infusion-related reaction, the following prophylactic premedications are recommended: diphenhydramine 50 mg (or equivalent) and/or acetaminophen 325 to 1000 mg (or equivalent), administered at least 30 minutes prior to the infusion. If necessary per the judgment of the treating investigator, corticosteroids (up to 25 mg SoluCortef or equivalent) may be used.

5.4.2 Drug-Drug Interaction Potential with Nivolumab

Although monoclonal antibodies are not direct inhibitors/inducers of metabolizing enzymes, recent literature reports suggest that therapeutic proteins that are modulators of cytokines may indirectly affect expression of cytochrome (CYP) enzymes. The indirect drug-drug interaction potential of nivolumab was assessed using systemic cytokine modulation data for cytokines known to modulate CYP enzymes, at single and multiple doses of 0.3 to 10 mg/kg Q3 weeks.

There were no meaningful changes in cytokines known to have indirect effects on CYP enzymes across all dose levels of nivolumab (0.3, 2 and 10 mg/kg) during the course of treatment. This lack of cytokine modulation suggests that nivolumab has no or low potential for modulating CYP enzymes, thereby indicating a low risk of therapeutic protein-drug interaction.

Nivolumab is an IgG4 monoclonal antibody, which is eliminated by mechanisms similar to that of other antibodies, namely by non-specific catabolism (mainly by enzymes in the reticuloendothelial system). These enzymes are not known to be inhibited or induced by drugs, and therefore it is unlikely that other drugs will have an impact on the PK of nivolumab.

5.4.3 Drug-Drug Interaction Potential with Ipilimumab

Ipilimumab is a human monoclonal antibody that is not metabolized by cytochrome P450 enzymes (CYPs) or other drug metabolizing enzymes.

A drug-interaction study of ipilimumab administered alone and in combination with chemotherapy (dacarbazine or paclitaxel/carboplatin) was conducted evaluating interaction with CYP isozymes (particularly CYP1A2, CYP2E1, CYP2C8, and CYP3A4) in patients with treatment-naïve advanced melanoma. No clinically relevant pharmacokinetic drug-drug interaction was observed between ipilimumab and paclitaxel/carboplatin, dacarbazine or its metabolite, 5-aminoimidazole-4-carboxamide (AIC).

The use of anticoagulants is known to increase the risk of gastrointestinal hemorrhage. Since gastrointestinal hemorrhage is an adverse reaction with ipilimumab, patients who require concomitant anticoagulant therapy should be monitored closely.

5.5 Criteria for Taking a Participant Off Protocol Therapy

Duration of therapy will depend on individual response, evidence of disease progression and

tolerance. In the absence of treatment delays due to adverse event(s), treatment may continue for a maximum of 24 months or until one of the following criteria applies:

- Disease progression, unless the participant meets the requirements outlined in **Section 5.5.1**.
- Intercurrent illness that prevents further administration of treatment
- The patient becomes pregnant or plans to become pregnant
- Unacceptable adverse event(s)
- Participant decides to withdraw from the protocol therapy
- General or specific changes in the participant's condition render the participant unacceptable for further treatment in the judgment of the treating investigator

Participants will be removed from the protocol therapy when any of these criteria apply. The reason for removal from protocol therapy, and the date the participant was removed, must be documented in the case report form (CRF). Alternative care options will be discussed with the participant.

When a participant is removed from protocol therapy and/or is off of the study, the relevant Off-Treatment/Off-Study information will be updated in OnCore.

In the event of unusual or life-threatening complications, treating investigators must immediately notify the Overall PI, [name] at [contact].

5.5.1 Treatment Beyond Disease Progression

Accumulating evidence indicates a minority of subjects treated with immunotherapy may derive clinical benefit despite initial evidence of progressive disease (PD)¹⁶.

Subjects will be permitted to continue on nivolumab and ipilimumab for treatment beyond initial RECIST 1.1 defined PD as long as they meet all of the following criteria:

1. Investigator-assessed clinical benefit and no rapid disease progression or threat to vital organs/critical anatomical sites requiring urgent alternative medical intervention (e.g. spinal cord compression)
2. Subject is tolerating study treatment
3. Subject has a stable performance status
4. Treatment beyond progression will not delay an imminent intervention to prevent serious complications of disease progression (e.g. CNS metastases)
5. Subject provides written informed consent prior to receiving additional nivolumab and ipilimumab treatment.

The decision to continue treatment beyond initial investigator-assessed progression should be

discussed with the principal investigator and documented in the study records. A follow-up scan should be performed in six (6) weeks \pm 7 days of original PD to determine whether there has been a decrease in the tumor size, or continued progression of disease. Subsequent scans should be performed as per protocol criteria.

If the investigator feels that the subject continues to achieve clinical benefit by continuing treatment, the subject should remain on the trial and continue to receive monitoring according to the Study Calendar located in **Section 10**.

For the subjects who continue study therapy beyond progression, further progression is defined as an additional 10% increase in tumor burden from time of initial PD. This includes an increase in the sum of diameters of all target lesions and/ or the diameters of new measurable lesions compared to the time of initial PD. Nivolumab and ipilimumab treatment should be discontinued permanently upon documentation of further progression.

New lesions are considered measurable at the time of initial progression if the longest diameter is at least 10 mm (except for pathological lymph nodes which must have a short axis of at least 15 mm). Any new lesion considered non-measurable at the time of initial progression may become measurable and therefore included in the tumor burden if the longest diameter increases to at least 10 mm (except for pathological lymph nodes which must have a short axis of at least 15 mm). In situations where the relative increase in total tumor burden by 10% is solely due to inclusion of new lesions which become measurable, these new lesions must demonstrate an absolute increase of at least 5 mm.

5.6 Duration of Follow Up

Participants will be followed for a minimum of 90 days following their last dose of ipilimumab and 100 days following their last dose of nivolumab for serious adverse event (SAE) reporting. Participants removed from protocol therapy for unacceptable adverse event(s) will be followed at minimum until resolution or stabilization of the adverse event. Participants who are removed before documented disease progression should be followed for RECIST response criteria until disease progression or death. Following documentation of disease progression, participants will continue to be followed for a maximum of 3 years or until death for survival status only.

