5.7 Criteria for Taking a Participant Off Study

Participants will be removed from study when any of the following criteria apply:

- Lost to follow-up
- Withdrawal of consent for data submission
- Death
- Completion of required 3 years follow-up

The reason for taking a participant off study, and the date the participant was removed, must be documented in the case report form (CRF).

The research team will update the relevant Off Study information in OnCore.

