
A. A \pm 3 day scheduling window exists for this visit to accommodate vacations, holidays, adverse weather, or other scheduling difficulties.
 
B. The start of a subsequent cycle may be delayed by 7 days (+7 day window) to accommodate vacations, holidays, adverse weather, or other scheduling difficulties. The start of a subsequent cycle may also be moved up by 3 days (-3 day window) for scheduling issues.
 
C. Off-treatment evaluation. Note: follow up visits or other contact is required in order to identify SAEs during the 90 days following the last dose of ipilimumab and 100 days following the last dose of nivolumab. Participants removed from therapy due to adverse events must be followed at minimum until resolution or stabilization of the adverse event. Please refer to Section 5.6 for more detail.
 
D. Long-term follow up evaluation via telephone or care provider contact is required for survival status only for 3 years following documentation of disease progression, or until death. Contact to be performed every 3 months following the last dose of study treatment (\pm 1 month window).
 
E. Vital signs to include heart rate, blood pressure, temperature, and respiratory rate.
 
F. Serum chemistry to include sodium, potassium, chloride, CO₂, blood urea nitrogen (BUN), creatinine, glucose, albumin, total protein, alkaline phosphatase, total bilirubin, SGOT [AST], and SGPT [ALT]. Other tests may be ordered as clinically indicated.
 
G. Serum pregnancy test only required for women of childbearing potential. Childbearing potential defined as any female who has experienced menarche and who has not undergone successful surgical sterilization (hysterectomy, bilateral tubal ligation, or bilateral oophorectomy) or is not postmenopausal (defined as amenorrhea >12 consecutive months; or women with a documented plasma follicle-stimulating hormone level $>35\mu\text{IU}/\text{mL}$).
 
H. Nivolumab and ipilimumab infusions to be administered as described in Section 5.
 
I. Fresh tumor tissue biopsy as described in Section 9. Biopsy required at baseline prior to the administration of any study agents, and again on Cycle 1 Day 29 (\pm 7 day scheduling window). An optional biopsy at the time of disease progression will also be offered to all participants. Note that a germline blood sample is required with the pre-treatment tumor biopsy as described in Section 9.
 
J. PBMC collection to occur at baseline (any time prior to the first study drug administration), on Cycle 2 Day 1, and at the off treatment visit as described in Section 9.
									

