13.2 Sample Size, Accrual Rate and Study Duration

A maximum total of 80 participants will be enrolled to the trial. We anticipate accruing approximately 3 – 4 subjects per month. Up to an additional three years of follow-up will be required on the last participant to observe response to trial therapy, for a total study length of approximately 6 years.

Table 19: Accrual Targets

Ethnic Category	Sex/Gender			Total
	Females	Males		
Hispanic or Latino	2	+	1	= 3
Not Hispanic or Latino	39	+	38	= 77
Ethnic Category: Total of all subjects	41	(A1)	39	(B1) = 80 (C1)
Racial Category				

American Indian or Alaskan Native	0	+	0	=	0
Asian	1	+	0	=	1
Black or African American	0	+	2	=	2
Native Hawaiian or other Pacific Islander	0	+	0	=	0
White	40	+	37	=	77
Racial Category: Total of all subjects	41	(A2)	39	(B2)	80
		(A1 = A2)		(B1 = B2)	
					(C1 = C2)

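### Survival follow-up ends 3 years after progression, so Kaplan-Meier OS beyond 36 months rests on censoring that is not independent of outcome

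*Combined protocol and SAP*

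**What the plan says.** Four places deal with the length of follow-up.

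- Section 5.6: once progression is documented, "participants will continue to be followed for a maximum of 3 years or until death for survival status only". Participants who stop treatment before progression are followed for response until progression or death, with no time limit.
- Table 16 note D (section 10): long-term contact "is required for survival status only for 3 years following documentation of disease progression, or until death". The contact interval has a different origin: "Contact to be performed every 3 months following the last dose of study treatment".
- Section 5.7 lists among the reasons for going off study "Completion of required 3 years follow-up", without saying when the 3 years begin.
- Section 13.2: "Up to an additional three years of follow-up will be required on the last participant to observe response to trial therapy", with a total study length of about 6 years.

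Section 13.1.1 defines OS from registration and censors living participants at the last contact. Section 13.1.3 estimates OS by Kaplan-Meier and makes no provision for a follow-up limit tied to progression. OS is a secondary endpoint.

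**The concern.** Kaplan-Meier assumes that participants censored at a given time have the same later prognosis as those who remain at risk. Under 5.6, follow-up of a living participant ends at a time fixed by the date of progression, which is itself an outcome related to survival. After month 36 early progressors who are alive leave the risk set, while late progressors and progression-free participants stay in it. The later part of the OS curve, which is of interest with immunotherapy, then describes a selected group. Because the direction of the selection is not known in advance, a reader could not correct the reported tail afterwards.

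A second, administrative matter is that the sections do not give a site or an analyst one clear date on which survival follow-up ends.

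**Working it through.** **When the limit acts.** For a living participant who progresses T months after registration, the last survival contact under 5.6 is at T + 36 months. Illustrations: T = 3 gives month 39; T = 24 gives month 60; no progression gives no limit. Since T is positive, the limit cannot act before month 36.

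**Study length.** The plan's figure is about 6 years. Accrual of 80 at 3 to 4 per month (13.2) takes 80/4 = 20 to 80/3 = 26.7 months. Adding follow-up of the last participant:

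- 3 years from last registration: 20 + 36 = 56 to 26.7 + 36 = 62.7 months, or 4.7 to 5.2 years.
- The 5.6 rule, with progression at an assumed median. Arm Q in Table 2 has 12-month PFS of 35%; if PFS is exponential, the median is 12 × ln 2 / (−ln 0.35) = 7.9 months. Then 20 + 7.9 + 36 = 63.9 to 26.7 + 7.9 + 36 = 70.6 months, or 5.3 to 5.9 years.
- The 5.6 rule, with progression at 24 months: 20 + 24 + 36 = 80 to 26.7 + 24 + 36 = 86.7 months, or 6.7 to 7.2 years.
- The 5.6 rule, with no progression: no end date.

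The stated figure is not reproduced exactly, but it is nearly met if the last participant progresses near the assumed median.

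**Size of the error.** Registration, progression and death were simulated for 400,000 patients, matched to arm Q (12-month PFS 35%, median OS 18.1 months). Assumptions not in the documents: exponential PFS with or without a 15% progression-free plateau, 10% of PFS events being deaths, four shapes of survival after progression, and 24-month accrual. OS at 60 months, in percent:

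| Survival after progression | Plateau | True | Kaplan-Meier under 5.6 | Error |
|---|---|---|---|---|
| Constant hazard | none | 3.2 | 3.4 | +0.2 |
| Constant hazard | 15% | 16.3 | 18.1 | +1.8 |
| Falling hazard (Weibull shape 0.6) | none | 10.4 | 9.4 | −1.0 |
| Falling hazard (Weibull shape 0.6) | 15% | 21.6 | 24.4 | +2.8 |
| 15% long survivors | none | 7.8 | 6.3 | −1.5 |
| 15% long survivors | 15% | 20.4 | 21.9 | +1.5 |
| Mean rising with PFS | none | 15.1 | 16.7 | +1.6 |
| Mean rising with PFS | 15% | 23.7 | 26.1 | +2.4 |

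At 36 months there was no error. Between 4% and 18% of patients reached the limit; about 2 to 9 of 80 would be censored by it before a 6-year cutoff. With a common calendar cutoff in place of the limit, Kaplan-Meier stayed within about 0.3 points of the truth in every scenario.

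Two further simulations under other assumed models bear on the range. Shared gamma frailty (variance 0.3 to 1.0, median PFS 6 months, about 12 months' survival after progression) gave 16.3% true against 18.3%, and 32.2% against 35.0%, at 60 months. Another set of models gave −0.4 to +1.7 points at 48 months and −1 to +3.6 at 58 months.

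**Against the planned precision.** Section 13.1.3 plans two-sided 80% intervals. With all 80 fully followed, the half-width is 1.28 × √(S(1 − S)/80). For S = 0.163 to 0.322, the frailty values at 60 months, this is 5.3 to 6.7 points. Real intervals would be wider.

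**The case against.** The strongest defence is that little depends on this. OS is secondary, no 4- or 5-year OS landmark is named, and the limit cannot affect anything up to month 36. Even near 5 years the error is smaller than the half-width of an 80% interval. All of that stands and keeps the point minor. It does not make the censoring independent.

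Three stronger readings are tempting, and the documents do not support them.

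- *The OS tail is overstated.* The sign depends on the survival pattern. With a progression-free plateau the limit left better-prognosis patients at risk, and the tail was too high in every scenario. Where hazard falls after progression and there is no plateau, those removed are long post-progression survivors with low hazard, and the tail was too low. The documents do not say which pattern will apply.
- *Section 5.7 contradicts 5.6 and would remove progression-free participants at 3 years.* That requires a start at registration, which 5.7 does not state. It follows 5.6 directly and can be read as pointing back to the same 3 years. It is ambiguous, not contradictory. If it did mean 3 years from registration, all living participants would be censored alike at 36 months and this bias would not arise.
- *Section 13.2 is wrong.* It is a planning estimate, worded as an upper bound on follow-up and an approximate total, and the central case gives 5.3 to 5.9 years. What remains is that 5.6 sets no fixed end for a late progressor or for a participant who never progresses.

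**Conclusion.** The point holds as a minor one. As 5.6 and Table 16 note D are written, OS censoring after month 36 depends on the date of progression, and the planned Kaplan-Meier estimate does not allow for that. The error is about −1.5 to +3.6 points near 5 years, upward in 6 of the 8 tabulated scenarios but of uncertain sign. These sizes rest on assumed shapes for PFS and post-progression survival that the documents do not supply; the dependence itself follows from the text. OS to 36 months, the primary response rate and the two-stage decision are unaffected, as is median OS if it falls before month 36 (18.1 months in arm Q). The missing starting point in 5.7 and the lack of a fixed end consistent with 13.2 are matters of clarification.

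**What to change.** Use one rule in 5.6, 5.7, Table 16 note D and 13.2: every participant is followed for survival until death, withdrawal, loss to follow-up, or one common calendar cutoff that does not depend on progression. An example is the planned study end, about 6 years from first registration. At the planned accrual the last participant would then have 72 − 26.7 = 45.3 to 72 − 20 = 52 months of follow-up. Restate the study length to match.

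A cutoff 3 years after last registration would also remove the dependence, but it falls at month 56 to 62.7. At 4 per month nobody could reach 60 months. At 3 per month only those registered in the first 2.7 months could, about 2.7 × 3 = 8 participants.

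If the present rule is kept, censor and report OS at 36 months from registration, and state the starting point in 5.7.

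The cost is amendment wording and extra 3-monthly telephone contacts for early progressors who are still alive. A common cutoff also shortens follow-up for some late-enrolled participants compared with 5.6 taken literally. A last registrant who progresses at 24 months could be followed to month 60 under 5.6, to month 45 to 52 under the 6-year cutoff, and only to month 36 under the earlier one.
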